Title: Adjunctive Anti-Obesity Pharmacotherapy in Adolescents and Young Adults after Bariatric Surgery: A Randomized Controlled Pilot Study

NCT#: NCT04095104

Document Version Date: 07/21/2021

COMIRB Protocol

COLORADO MULTIPLE INSTITUTIONAL REVIEW BOARD [name] [contact] [contact]

Protocol #: 18-2793

Project Title: Adjunctive Anti-Obesity Pharmacotherapy in Adolescents and Young Adults after

Bariatric Surgery: A Randomized Controlled Pilot Study

Principal Investigator: [name]

Co-Investigators: [name]; [name] PhD; [name]; [name]

Version Date: 7/21/21

I. Hypotheses and Specific Aims:

Primary Aim 1: Assess the feasibility (including protocol implementation and acceptability) of a randomized, placebo-controlled, double-blinded, adjunctive 12-week phentermine + topiramate intervention beginning 6-12 months after bariatric surgery, among adolescents and young adults (age 12-24 years) who don't achieve expected weight loss or who remain severely obese (n=14 total). **Hypothesis 1**: Protocol implementation, including recruitment and retention, will be feasible based on achievement of adequate enrollment and participant completion of at least 80% of study visits. The experimental group will report better acceptability compared to the control group based on satisfaction with the desired effects of the active drugs.

Secondary Aim 2: Test the initial efficacy of standard of care plus 12 weeks of active drugs or placebo on percent weight loss beginning 6 to 12 months postoperatively.

Hypothesis 2: The experimental group will experience a greater percent weight loss than the control group at the end of the 12 week intervention period.

Secondary Aim 3: Evaluate the initial effects of standard of care plus 12 weeks of active drugs or placebo on cardiometabolic, eating behavior, and quality of life outcomes beginning 6 to 12 months postoperatively.

Hypothesis 3: The experimental group will demonstrate greater improvements than the control group in blood pressure (BP), lipids, alanine aminotransferase (ALT), hemoglobin A1c (HbA1c), and fat mass reduction; and, will report less hunger, increased satiety, more cognitive restraint, decreased daily caloric intake, increased resting metabolic rate, and better quality of life at the end of the 12 week intervention period.

II. Background and Significance:

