In addition to the above in-person study visits and designated remote data collection, there are eight standard study phone calls in the protocol:

- Phone Call 1: 1-2 days before the Screening/Enrollment Visit 0 (Reminder to fast)
- Phone Call 2: 1 week before Visit 1 (Phone Call Script 1)
- Phone Call 3: 1 week after Visit 1 (Phone Call Script 2)
- Phone Call 4: 2 weeks after Visit 1 (Phone Call Script 2)
- Phone Call 5: 3 weeks after Visit 1 and 1 week before Visit 2 (Phone Call Scripts 1 & 2)
- Phone Call 6: 1 week before Visit 3 (Phone Call Script 1)
- Phone Call 7: 1 week before Visit 4 (Phone Call Script 1)
- Phone Call 8: 1 week after last dose of study drug (Phone Call Script 2)

If a participant requires additional dose titration during the protocol, the PI will conduct additional weekly phone calls until study medication dosage is stable.

E. Potential Scientific Problems:

Benchmarks for success, pitfalls, and alternatives:

Primarily, we expect this protocol to demonstrate feasibility, which will form the foundation for a larger study of pharmacotherapy as an adjunct to bariatric surgery. Secondarily, we expect to demonstrate short-term efficacy of pharmacotherapy in terms of promoting additional weight loss and improving biological markers.

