Sample size justification: Based on recommended practice for pilot studies, 60 the minimum sample size (10 total participants, 5 per arm) is driven by the primary aim of the study and represents a balance between participant availability (patient volume and recruitment timeline), and acceptable precision around feasibility estimates (Aim 1), which will be used for subsequent study planning. It is not based on a power calculation for group differences seen in any Aim 2 or 3 measures. To estimate precision around dropout and medication tolerability rates, we used a confidence interval approach with normal approximation of the binomial calculation 60-62. First, we estimate that a realistic dropout rate is 25%, based on 3 prior anti-obesity medication RCTs conducted in obese adolescents. 22,63,64 A realistic medication tolerability rate (% who do not discontinue medication because of adverse effects) is 85%, based on the single RCT of topiramate in adolescents and two larger RCTs of phentermine/topiramate XR in adults. ^{22,65,66} Dropout: With the minimum of 10 adolescent/young adult participants, if our observed dropout rate is 25%, we can be 68% confident that the enrollment rate estimate is accurate within 13 percentage points (or 90% confident that it is accurate within 20%). With 14 adolescent/young adult participants, if our observed dropout rate is 25%, we can be 68% confident that the enrollment rate estimate is accurate within 11 percentage points (or 90% confident that it is accurate within 18%). Medication tolerability: With 10 adolescent/voung adult participants, if our observed medication tolerability rate is 85%, we can be 68% confident that the tolerability estimate is accurate within 9 percentage points (or 90% confident that it is accurate within 16%). With 14 adolescent/young adult participants, if our observed medication tolerability rate is 85%, we can be 68% confident that the tolerability estimate is accurate within 9 percentage points (or 90% confident that it is accurate within 15%). Given possible constraints around enrollment, the level of precision with 10 or 14 adolescents/young adults was deemed acceptable to achieve protocol refinement for future RCT development.

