Planned analyses: Descriptive statistics will characterize the study population. Independent samples t-tests will be performed for continuous variables and chi-square for categorical variables to determine statistically significant differences between experimental and control groups. Aim 1: Feasibility of acceptability (adherence, tolerability, and satisfaction) will be descriptively assessed using differences in proportions between experimental and control groups. Feasibility of protocol implementation will be established by determining the proportions (rates) of recruitment, enrollment, randomization, and dropout. Aims 2,3: Estimated means and variability of continuous health outcome variables (e.g. % change in weight) and intra- and intersubject variability of repeated measures (e.g. loss of control eating) will be graphically presented and visually compared for experimental vs. control groups, as this aim is not powered to run inferential statistics.

G. Summarize Knowledge to be Gained:

The goal of this study is to establish the feasibility and initial efficacy of two common anti-obesity medications for adolescents who require additional risk reduction following bariatric surgery.

Adolescents with severe obesity who don't achieve optimal weight loss and co-morbidity improvement after bariatric surgery have few evidence-based treatment options to mitigate significant health risks through the remainder of adulthood. This study has the potential for substantial impact regardless of results, given that anti-obesity medications are currently being used in the post bariatric surgery setting without an evidence base. A recent international pediatric obesity webinar (4/2019) with contributors from leading adolescent bariatric surgery centers strongly expressed need and enthusiasm for studying the role of pharmacotherapy after surgery. Our center's volume, interdisciplinary expertise, and existing IND to study these medications in this setting sets us apart as the best positioned adolescent bariatric surgery center to carry out this initial pilot, with high potential for a subsequent larger multi-site RCT to evaluate safety and efficacy, mechanism of action, and predictors of response.

H. References:

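### Hypothesis 2 (greater 12-week weight loss) is left to a visual comparison with no planned between-arm difference or interval, while significance tests are ordered on unnamed variables

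*Combined protocol and SAP*

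**What the plan says.** Section I sets Secondary Aim 2 as "Test the initial efficacy of standard of care plus 12 weeks of active drugs or placebo on percent weight loss". Hypothesis 2 follows: "The experimental group will experience a greater percent weight loss than the control group at the end of the 12 week intervention period".

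Section IV.F, under Planned analyses, makes three statements that bear on this:

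- After a sentence on describing the study population, it orders independent-samples t-tests for continuous variables and "chi-square for categorical variables to determine statistically significant differences between experimental and control groups". It gives no variables, time point, significance level or sidedness.
- Aim 1 acceptability "will be descriptively assessed using differences in proportions between experimental and control groups".
- For Aims 2 and 3, arm means and variability (percent change in weight is the example) are to be "graphically presented and visually compared for experimental vs. control groups, as this aim is not powered to run inferential statistics".

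Under Sample size justification, the same section says of the Aim 1 rates: "we used a confidence interval approach with normal approximation of the binomial calculation". It also states that the trial was not sized on power for any Aim 2 or 3 measure.

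Section IV.E says that, secondarily, "we expect to demonstrate short-term efficacy of pharmacotherapy in terms of promoting additional weight loss and improving biological markers". Section IV.G gives establishing initial efficacy, alongside feasibility, as the goal of the study.

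**The concern.** There are two linked faults in one paragraph.

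First, Hypothesis 2 concerns a difference between arms, and the plan never states that difference or its uncertainty. With 5 to 7 patients per arm, two plotted means will differ by chance, often by an amount that looks meaningful. Section IV.E has already announced that efficacy is expected, so such a gap can be read as confirmation. A planned interval beside the graph would show how little the data can exclude.

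Second, the significance-testing sentence has no clear object. Aim 1 is called descriptive and Aims 2 and 3 are excluded from inference, so no named outcome is left to test. Its position makes baseline characteristics the likelier reading. In that case the tests examine differences that 1:1 randomisation has already made chance ones. On the less likely reading, as outcome tests, they conflict with the statement that Aims 2 and 3 are not powered for inference. On either reading chi-square is being applied to very small cells.

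**Working it through.** The documents give no SD, effect size, significance level or interval for Aim 2, so there is no planned figure to reproduce.

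**Inputs**
- 14 participants, 7 per arm, randomised 1:1 (Section IV.B).
- Minimum of 10, 5 per arm (Section IV.F).
- Dropout: the plan says "we estimate that a realistic dropout rate is 25" per cent (Section IV.F). 14 × (1 − 0.25) = 10.5, so about 5 per arm is the case to expect. Section IV.D keeps participants who stop drug in follow-up, with their consent, so 7 per arm is also shown.
- SD of 12-week percent weight change: assumed 3 to 6 percentage points.

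**Precision of the between-arm difference**

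Half-width of the 95% interval = t(0.975, 2n − 2) × SD × √(2/n). One standard error = SD × √(2/n).

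| Per arm | t | √(2/n) | Half-width | SD 3 | SD 6 | One SE, SD 3 to 6 |
|---|---|---|---|---|---|---|
| 7 | 2.179 | 0.5345 | 1.16 SD | ±3.5 points | ±7.0 points | 1.6 to 3.2 points |
| 5 | 2.306 | 0.6325 | 1.46 SD | ±4.4 points | ±8.8 points | 1.9 to 3.8 points |

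**What chance alone shows.** With no true effect, the active arm has the better mean half the time. A gap of more than one standard error in either direction has probability P(|Z| > 1) = 0.32 by the normal approximation, about one trial in three. Half of that, about 16%, favours the active drug.

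**Whether testing would have helped.** At an assumed two-sided 5% level, a t-test has 80% power only for differences of about 1.6 SD (7 per arm) or 2.0 SD (5 per arm). The plan is right not to test efficacy.

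**Chi-square cells.** With equal arms, a two-level variable with k of N participants in one level has expected counts k/2 and (N − k)/2 in each arm.
- N = 14: the rarer level has k ≤ 7, so its expected count is at most 7/2 = 3.5.
- N = 10: the rarer level has k ≤ 5, so its expected count is at most 5/2 = 2.5. For any k from 1 to 9 the larger count is at most 9/2 = 4.5, so all four cells are below 5.

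The usual guide of 5 per cell therefore fails for every two-level variable at either size.

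**The case against.** The best defence is that this is a feasibility pilot whose descriptive treatment of efficacy is deliberate and disclosed. Arm means and variability are planned. They supply the SD that a later trial needs, and a reader can derive the interval from them and the arm sizes. All of this is true, and it is why the point is small.

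Four further objections have some force:

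- A 95% t-interval excludes zero exactly when a two-sided 5% t-test rejects, so an interval could bring back the inference the plan declined. It also shows the range of effects compatible with the data, which neither a test result nor a plot of two means states.
- The Aim 1 intervals are 68% and 90% planning precision for single proportions, not a rule for reporting contrasts. They show only that the plan accepts interval reasoning at n = 10 and n = 14. The between-arm differences planned for acceptability are the closer precedent.
- The efficacy language is qualified: it is secondary, it is called initial, and Section IV.E leaves efficacy as a primary aim to future studies. These limits reduce the risk of over-reading but do not supply the missing contrast.
- If the tests concern baseline only, they do not bear on Hypothesis 2. That is so; they are a separate, minor fault in the same paragraph, and naming the variables would remove the ambiguity but not the small cells.

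**Conclusion.** The concern holds, as an inexpensive improvement and not a threat to the trial. No section plans a between-arm difference or interval for Hypothesis 2, and the testing sentence is unsuitable on either reading. The half-widths of 1.16 SD and 1.46 SD assume equal arms, a common SD and a t-based interval. The percentage-point figures rest on the assumed SD of 3 to 6 points and scale with it. The 95% level is a choice made here; at 90% the half-widths are 0.95 SD and 1.18 SD. The absence of a stated difference or interval is certain. That the tests are meant for baseline is only the likelier reading.

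**What to change.** In Section IV.F, delete the sentence ordering t-tests and chi-square tests and state that baseline characteristics will be described by arm. For Aim 2, add the unadjusted between-arm difference in mean 12-week percent weight change, with a 95% confidence interval, the number per arm with a 12-week weight, and no p-value. Label it exploratory and place it beside the planned graphs.

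As a lesser matter, in Section IV.E word the efficacy expectation as estimation and not demonstration, and present the look at the two eligibility subgroups as description.

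The cost is one rewritten paragraph and one extra line of output, with no additional data or visits. The interval will be visibly wide, and some readers may take one that includes zero as a negative result. The exploratory label limits that risk.

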Fourteen patients (7/arm) followed in the Children's Hospital Colorado Bariatric Surgery Center who meet inclusion criteria: 12-24yo; s/p SG or RYGB; and at 6-12 months post bariatric surgery^a, have either a) not achieved mean expected weight loss based on national standards and still have at least class 1 obesity or b) remain severely obese (\geq 120% of 95%ile or BMI \geq 35kg/m2 for 12-17yo; BMI \geq 35kg/m2 for 18-24yo) will be randomized 1:1 to pharmacotherapy + SOC^b or placebo + SOC in double-blind fashion. Expected weight loss at 6, 9, and 12 months postoperatively will be defined as a \geq 26%, \geq 28%, and \geq 31% decrease in weight, respectively, from preoperative weight (within 1 week of surgery) as was observed in the Teen-LABS study.⁷

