- There will be a screening visit at 6, 9, or 12 months postoperatively. Eligible participants will be consented at this visit, and will be asked to come to campus ~1 week later for study visit 1. Enrollment and Visit 1 cannot be combined because it is unrealistic to screen, consent, randomize, obtain study drug, and complete additional measures after an already lengthy clinical appointment.
- The Children's Hospital Colorado Lifestyle Medicine weight management program's clinical protocols for anti-obesity pharmacotherapy require monthly clinic visits for the first three months after initiation for monitoring of effects and side effects. The proposed study protocol follows this standard.

Data Collection Tools (See Table 3. below for Schedule of Measures)

- a) Sociodemographic characteristics: age, sex, race/ethnicity, insurance, highest level of primary caregiver's education, household size and income, government-based assistance, and presence/absence of food insecurity will be obtained from the medical record and the Demographics Form.
- b) Feasibility of protocol implementation: rates of recruitment, enrollment, randomization, and dropout
- c) Study medication adherence & tolerability: assessed by 1) Questionnaire: description/dose/start date of medications, missed doses, and checklists of: effects, adverse effects, and evidence-based barriers to adherence^{51,52}; 2) Pill counts; 3) Urine amphetamine screen
- d) Self-reported changes to all non-study medications: name/dose, interim changes
- e) Patient/family satisfaction questionnaire will assess: reasons for participation, experience during study visits, satisfaction with the effect of the study medication/placebo, ease of communication with study staff, and time burden/inconvenience
- f) Biological outcome and safety measures: Weight, height, heart rate (HR), BP, basic metabolic panel, lipids, ALT, HbA1c, and pregnancy test
- g) Optional Biobanking: Gold top (serum-3.5mL blood), Purple top (EDTA-4mL whole blood), Green top (heparinized plasma-4mL blood), and Urine (volume that remains after the urine pregnancy test for females and a separate urine collection for males) will be collected with participant assent/consent for future research questions.
- h) 3-day dietary record: Participants will complete a dietary record on 3 consecutive days (2 weekday, 1 weekend day) based on standardized protocols for dietary assessment.⁵³

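### The Aim 3 plan names no baseline adjustment and does not say whether Visit 4 values or changes are summarised, so chance baseline differences at 5 to 7 per arm can colour the comparison

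*Combined protocol and SAP*

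**What the plan says.** Section IV.F (Data Analysis Plan, Planned analyses) treats Aims 2 and 3 in one sentence. Means and variability of the continuous outcomes, and within- and between-subject variability of repeated measures, "will be graphically presented and visually compared for experimental vs. control groups". The stated reason is that the aim is not powered for inference. The only continuous example given is percent change in weight. The form of the Aim 3 summaries is not stated, and no baseline adjustment is named. The t-tests mentioned earlier in that paragraph follow directly on the description of the study population and are also unadjusted.

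Section I, Hypothesis 3, is framed as improvement: "The experimental group will demonstrate greater improvements than the control group in blood pressure (BP), lipids", followed by ALT, HbA1c, fat mass, hunger, satiety, restraint, caloric intake, resting metabolic rate and quality of life.

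The data for an adjustment are already planned. The Data Collection Tools list includes "Weight, height, heart rate (HR), BP, basic metabolic panel, lipids, ALT, HbA1c, and pregnancy test". Table 3 places lipids, ALT and HbA1c at Enrollment and Visit 4. It places blood pressure, DEXA, resting metabolic rate, diet record, eating-behaviour questionnaires and quality of life at Visit 1 and Visit 4, some of them at Visits 2 and 3 as well.

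On size, section IV.B has "Fourteen patients (7/arm) followed in" the centre's bariatric programme, who "will be randomized 1:1 to pharmacotherapy + SOC" or to placebo, with no stratification described. Section IV.F adds that "the minimum sample size (10 total participants, 5 per arm) is driven by the primary aim of the study".

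**The concern.** With 5 to 7 people per arm, randomisation will often leave the arms some distance apart before the first dose. A plot of Visit 4 means then carries part of that gap. A plot of changes carries regression to the mean, so the arm that starts worse tends to look as if it improved more. Because the plan does not fix which summary is used, the choice can also be made after the data are seen, outcome by outcome.

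What is at stake is how the Aim 3 displays are read. Section IV.E expects to show short-term efficacy, including on biological markers, and section IV.G gives initial efficacy as part of the study goal with a larger trial in view. A visible difference between arms may be taken as an early drug signal when part of it was there at baseline.

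**Working it through.** **The plan's own figures.** There is none for Aim 3. The only design figures are the Aim 1 half-widths, z × √(p(1−p)/n). With whole-patient counts (2/10, 3/14, 9/10, 12/14) they come to 12.6/20.8, 10.9/18.0, 9.4/15.6 and 9.3/15.4 points at 68%/90% confidence, against the stated 13/20, 11/18, 9/16 and 9/15. Seven of eight agree after rounding. They do not bear on this point.

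**Inputs.** n = 7 per arm (section IV.B) or 5 per arm (section IV.F minimum). The plan's assumed 25% dropout from 14 leaves 14 × 0.75 = 10.5, so about 5 per arm is also the plausible completer number. Outcome SDs and the baseline-to-Visit 4 correlation r are not in the documents. I work in SD units, assume equal SDs at the two times, and take r from 0.3 to 0.9.

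**Step 1: size of chance baseline gaps.** The SD of the difference in baseline means is √(2/n): √(2/7) = 0.535 and √(2/5) = 0.632. The probability of a gap of at least 0.5 SD is 2(1 − Φ(0.5/0.535)) = 35% and 2(1 − Φ(0.5/0.632)) = 43%. Counting blood pressure, lipids and quality of life once each, Hypothesis 3 lists 11 outcomes. The expected number starting at least 0.5 SD apart is 0.35 × 11 = 3.9 or 0.43 × 11 = 4.7, whatever the correlation among outcomes.

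**Step 2: what a gap does.** Given a baseline gap D, the expected Visit 4 difference shifts by rD and the expected difference in change by −(1 − r)D. For D = 0.5:

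| r | Visit 4 means | Change scores |
|---|---|---|
| 0.3 | +0.15 | −0.35 |
| 0.5 | +0.25 | −0.25 |
| 0.7 | +0.35 | −0.15 |
| 0.9 | +0.45 | −0.05 |

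Averaged over randomisations D is zero, so neither summary is biased. These are shifts conditional on the gap that occurred.

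**Step 3: precision.** The SE of the arm difference is √(2/n) for Visit 4 means, √(2/n) × √(2(1 − r)) for change, and √(2/n) × √((1 − r²)(1 + 1/(2n − 4))) for the adjusted difference. The last factor, 1.10 at n = 7 and 1.17 at n = 5, is the cost of estimating the slope in a small sample.

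| r | n = 7: Visit 4 / change / adjusted | n = 5: Visit 4 / change / adjusted |
|---|---|---|
| 0.3 | 0.535 / 0.632 / 0.535 | 0.632 / 0.748 / 0.652 |
| 0.5 | 0.535 / 0.535 / 0.486 | 0.632 / 0.632 / 0.592 |
| 0.7 | 0.535 / 0.414 / 0.400 | 0.632 / 0.490 / 0.488 |
| 0.8 | 0.535 / 0.338 / 0.336 | 0.632 / 0.400 / 0.410 |
| 0.9 | 0.535 / 0.239 / 0.244 | 0.632 / 0.283 / 0.298 |

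Over r = 0.5 to 0.8, adjustment lowers the SE against Visit 4 means by 9% to 37% (n = 7) or 6% to 35% (n = 5). Against change scores it runs from a 9% gain to about 0% (n = 7), or from a 6% gain to a 2.5% loss (n = 5). Across the whole table the adjusted SE is within about 0.02 SD of the better unadjusted choice. Each unadjusted choice is clearly worse somewhere: Visit 4 means at high r, change at low r.

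**Step 4: false appearances.** In 40,000 simulated trials per setting with no drug effect and r = 0.7, an apparent difference above 0.5 SD arose with Visit 4 means, change and adjustment in 35%, 22% and 21% of trials at n = 7, and in 43%, 30% and 30% at n = 5. At r = 0.3 adjustment gave no gain over Visit 4 means (35% and 35% at n = 7; 43% and 44% at n = 5).

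**The case against.** A reader might infer that the plan compares raw Visit 4 arm means. The text does not say so. Its one continuous example is a change from baseline, Hypothesis 3 speaks of improvement, and within-subject variability is to be shown. If change is what is meant, the larger precision gains above fall away. For stable measures adjustment then offers almost nothing in SE. At 5 per arm, counting the lost degree of freedom (t on 7 rather than 8 df), its 95% interval is about 2% wider than for change at r = 0.7 and 5% wider at r = 0.8. All of this stands.

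It is also fair that Aims 2 and 3 are secondary, unpowered and deliberately descriptive. What section IV.F commits to later planning is the feasibility estimates. Nothing in the documents says that Aim 3 signals will select the outcomes of the larger trial. A single pooled model also cannot serve weight-related quality of life, which uses the Kids form up to age 19 and the Lite form from 20.

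What the objection does not remove is that the form of the summary is left open, that r is unknown and will differ by outcome, and that either unadjusted form carries a chance gap in one direction or the other. Lack of power is a reason not to test. It is not a reason to leave a measured baseline difference in the estimate.

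**Conclusion.** The point holds in a limited form. The plan leaves the Aim 3 summary unspecified and unadjusted, with a pre-dose value at hand for every Hypothesis 3 outcome. At 7 (5) per arm, about one outcome in three (two in five) will start at least 0.5 SD apart, which moves the visible comparison by 0.05 to 0.45 SD depending on r and on the summary chosen.

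Two stronger conclusions are not supported: that the planned displays are biased, since under randomisation they are not on average, and that adjustment would make Aim 3 informative. At r = 0.7 the adjusted SE is still about 0.40 SD (n = 7) to 0.49 SD (n = 5). The benefit is protection from baseline imbalance when r is unknown, with little or no gain in precision over change scores. The figures rest on equal SDs at the two times and an assumed r of 0.3 to 0.9. The consequence is modest because the aim is secondary and exploratory.

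**What to change.** In section IV.F, for each continuous Aim 3 outcome measured with the same instrument in all participants:

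- Plot individual baseline-to-Visit 4 lines by arm.
- Report the between-arm difference at Visit 4 from a linear model with arm and the participant's own pre-dose value, as an estimate with its interval and no test.
- Name the pre-dose value used (Enrollment or Visit 1). Visit 1 questionnaires may be collected remotely within the same week, so state that the value must precede the first dose.

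Show weight-related quality of life separately for the Kids and Lite forms, as individual values without a pooled model.

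The cost is a few sentences of plan text and a few lines of code, with no new data. Each model spends one degree of freedom. At 5 per arm with high r, the interval will be slightly wider than for change scores. Aim 3 should still be labelled exploratory.
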